### 18.1.1. ALL AEs

All AEs will be summarized by PT, as well as by SOC and PT.

In addition, summary tables (by SOC and PT) will be generated for those AEs starting after the last dose of OLE study drug and those AEs starting more than 1 day after the last dose of OLE study drug.

The summary by SOC and PT will be broken down further by maximum severity and by strongest relationship to study medication. These summaries are described in the sections below.

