10.1.1. Dose Adjustment Criteria

All subjects will initiate treatment with SEP-4199 CR 200 mg/day. The dose may be increased to 400 mg/day at Visit 2E (Week 2/Day 14) or later, based on the Investigator's judgment. However, if clinically indicated, the dose may be increased as early as Day 7 at an unscheduled visit. The decision to increase the dose and dispense additional study drug will be made by the Investigator at a scheduled or unscheduled study visit. A dose decrease can occur at any time for safety or tolerability concerns (minimum dose of 200 mg/day). If a dose decrease is needed between study visits, subjects will return to the clinic for an unscheduled visit for drug dispensation. Temporary interruption of the study drug is allowed at the Investigator's discretion for specific hyperprolactinemia-related AESI (see Section 13.1).

Prior to a dose increase, safety assessments will be completed, including but not limited to evaluation of adverse events, concomitant medications, vital signs, and ECGs. Subjects whose ECG results, based on machine reading, show increase from Baseline in QTcF interval \geq 30 msec or whose QTcF interval is \geq 480 msec at the 200 mg/day dose are not allowed to have their dose increased to 400 mg/day. Subjects with hyperprolactinemia-related AESI are not allowed to have their dose increased to 400 mg/day. IXRS drug dispensing guidelines should be followed for dispensing the drug to subjects. A specific user manual will be provided.

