15.4.3.1. Adverse Events

All AEs will be coded using the Medical Dictionary for Regulatory Activities (MedDRA). Information on the format and version of the coding dictionary is provided in the DMP.

A treatment-emergent adverse event (TEAE) (hereafter referred to as AE) is an adverse event with onset data on or after the first day of the open-label treatment period through 7 days after study drug discontinuation (14 days for serious adverse events). The start of the open-label treatment period is defined as the first dose day for subjects previously randomized to placebo group and the OL Baseline visit date for subjects previously randomized to SEP-4199 CR groups.

The incidence of AEs, SAEs, and AEs leading to discontinuation due to AEs (or SAEs) will be summarized by analysis group (by presenting the number and percentage of subjects with one or more AEs in each category). The number and proportion of subjects with one or more AEs within a system organ class (SOC) and by preferred term (PT) will be presented by analysis group as well. The incidence of AEs (by preferred term, grouped by SOC) will also be summarized by severity, by the relationship to study medication, by the action taken regarding the study medication, as well as by the outcome. In addition, AEs will also be summarized by SOC, high-level term (HLT), and PT by presenting the number and percentage of subjects within each AE category.

The incidence of AESI, including but not limited to hyper-prolactinemia related AEs, will be summarized for overall and by gender as appropriate. For selected AESI, Kaplan-Meier curves will be plotted by analysis group for time to the earliest onsets. AEs associated with EPS will be summarized by analysis group.

Incidence of post-treatment adverse events (defined as an AE with a start date after the date of last dose of study drug through the last contact/visit in the follow-up period) will be summarized separately for subjects in the follow-up population.

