## 4.7. CHANGES TO ANALYSIS FROM PROTOCOL

Because of the small sample size due to study early termination, the following main changes will be made for this study:

- Only 2 treatment groups will be formed based on a subject's previous participation in the lead-in study of SEP-4199 CR (SEP-SEP: previously randomized to any SEP-4199 CR dose group and PBO-SEP: previously randomized to placebo).
- No subgroup summaries will be performed.
- No summaries using Follow-up population will be performed.
- Except for PWC, follow-up period summaries will not be performed, PWC will be summarized by Safety population.
- AE will not be summarized by high-level term (HLT).
- No Kaplan-Meier curves will be plotted for time to discontinuation and time to the earliest onsets of the selected AESI. The Kaplan-Meier estimation will also not be performed.
- To be consistent with AIMS and BARS, MSAS will be summarized by total score.

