### 18.1. ADVERSE EVENTS

Adverse Events (AEs) and pre-treatment events will be coded using MedDRA central coding dictionary, Version 22.0.

The concept of “pre-treatment events” only applies to study SEP380-301. Pre-treatment events are untoward medical occurrences that started prior to the first dose of study medication in SEP380-301.

Adverse events of study SEP380-301 are untoward medical occurrences that started at the same time of or after the first dose of study medication in SEP380-301, but before the first dose of OLE study medication in SEP380-303. These events will be recorded in the SEP380-301 databases.

Adverse events (AEs) of the SEP380-303 extension study are untoward medical occurrences that started at the same time of or after the first dose of the OLE study drug. These events will be recorded in the SEP380-303 database.

AEs (and pre-treatment events) that started in study SEP380-301 and are ongoing at the time of subject rollover will be re-entered into the SEP380-303 database and continue to be followed. These events will not be included in any AE summary table of SEP380-303. They will only be listed in a separate data listing.

Whenever available, the time information should be accounted for to determine if a record in the SEP380-303 AE database belongs to study SEP380-301 or SEP380-303. In the case where time is not available, untoward medical occurrences that started prior to the day of the first OLE dose will be considered to belong to study SEP380-301; those that started after the day of the first OLE dose will be considered to belong to study SEP380-303. Events that started on the same day of the first OLE dose will be assigned to study SEP380-301 or SEP380-303 depending on whether this AE record also exists in the SEP380-301 database (based on a comparison of subject ID, verbatim term, AE start date (and time if available), severity, and seriousness).

See [APPENDIX 2](#) for handling of partial dates for AEs.

Overall summary of the incidence of all AEs, study medication-related AEs, severe AEs, serious AEs, AEs leading to discontinuation from study, AEs leading to death, and AEs of special interest (AESI) will be provided by the actual treatment groups.

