#### 18.1.2. AEs LEADING TO DISCONTINUATION FROM STUDY

AEs leading to discontinuation from the study are those AEs with "Caused Study Discontinuation" = "Yes" on the "Adverse Events" CRF form for subjects with reason for discontinuation as AE on the Study Disposition CRF page or AE action taken = "Drug Withdrawn".

AEs leading to discontinuation from the study will be summarized by SOC and PT. A listing of AEs leading to discontinuation from the study treatment period will be presented.

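### The SAP drops the protocol's AE summaries by action taken and by outcome without declaring it, so no table it describes shows which AEs led to dose reduction or drug interruption

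*SAP*

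**What the plan says.** Protocol 15.4.3.1 plans further tables of AE incidence at the level of preferred term within system organ class (SOC), split in four ways: "by severity, by the relationship to study medication, by the action taken regarding the study medication, as well as by the outcome". The next sentence of that section adds a summary that includes the high-level term.

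Protocol 12.3 requires action taken with study treatment to be evaluated for every AE, in seven categories. Drug Interrupted and Dose Reduced are two of them. Protocol 10.1.1 makes both actions part of the design. On dose: "A dose decrease can occur at any time for safety or tolerability concerns (minimum dose of 200 mg/day". The same section allows temporary interruption, at the investigator's discretion, for specific hyperprolactinemia-related AESI.

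In SAP 18.1.1 the breakdown is narrower: "The summary by SOC and PT will be broken down further by maximum severity and by strongest relationship to study medication". Sections 18.1.1.1 and 18.1.1.2 specify those two tables, and no section specifies one by action taken or by outcome. The overall AE summary in SAP 18.1 starts with all, related, severe and serious AEs and ends: "AEs leading to discontinuation from study, AEs leading to death, and AEs of special interest (AESI) will be provided by the actual treatment groups".

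SAP 4.7 introduces its list with "the following main changes will be made for this study" and attributes the changes to the small sample after early termination. One of its seven items reads "AE will not be summarized by high-level term (HLT". Action taken and outcome do not appear among the seven.

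**The concern.** In a flexible-dose study, a poorly tolerated AE can be handled in three ways: stop the drug, interrupt it, or lower the dose. The protocol planned a table that separates these responses. The SAP describes a table for the first only. A reader of the study report could see how many subjects stopped because of an AE, but not how many had dosing reduced or paused because of one, or for which preferred terms.

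The omission is also hard to notice. SAP 4.7 names a dropped AE summary that sits next to these two in the protocol. Someone checking the SAP against the protocol would reasonably take it that the other AE breakdowns survive.

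**Working it through.** No sample size, power or event count is involved, so the check sets the sections side by side.

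**1. Breakdowns planned and kept**

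| Breakdown of AEs by SOC and preferred term | Protocol 15.4.3.1 | SAP 18.1.1 | Declared in SAP 4.7 |
|---|---|---|---|
| Severity | planned | kept | not needed |
| Relationship | planned | kept | not needed |
| Action taken | planned | absent | no |
| Outcome | planned | absent | no |
| High-level term | planned | absent | yes |

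Of the four breakdowns in the protocol sentence, 4 − 2 = 2 are gone, and neither is among the seven declared changes.

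**2. Use of the recorded fields**

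- *Action taken* (Protocol 12.3): seven categories, namely interrupted, withdrawn, reduced, increased, not changed, not applicable and unknown. SAP 18.1.2 uses withdrawn in defining AEs leading to discontinuation. The other 7 − 1 = 6 feed no table described in the SAP.
- *Outcome* (Protocol 12.3): six categories. SAP 18.1.3 uses fatal to define AEs leading to death. The other 6 − 1 = 5 feed no described table.

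**3. Can another summary supply the missing link?**

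- *Overall AE summary (SAP 18.1).* Its categories are all, related, severe, serious, leading to discontinuation, leading to death, and AESI. None concerns reduction or interruption.
- *Exposure (SAP 15 and 15.1).* Duration of exposure disregards missed doses and dose changes. Days at each dose level are the days on which the subject was expected to take that level. Mean and modal daily dose are also given. These describe the dosing received, but none is tied to an AE, so none shows why dosing changed.
- *Listings (SAP 18.1).* All AEs are listed by subject. The SAP text does not say whether action taken is a listed column, and a listing is not the planned incidence summary.

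**4. What is not lost**

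An AE managed by reduction or interruption still enters the all-AE tables, the severity and relationship tables and, where it qualifies, the severe, serious and AESI tables. The measures named in the primary objective (SAP 3.1.1) and the primary endpoints (SAP 3.2.1) are all retained.

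**The case against.** The strongest reply has four parts.

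- **Reduction and interruption are not endpoints.** The primary objective is defined through rates of AEs, AE discontinuations, SAEs and AESI, and all of these remain. Neither Protocol 6.1 nor SAP 3.2 lists AE-driven reduction or interruption. This stands, and it limits the weight of the point. It does not remove the commitment in Protocol 15.4.3.1.
- **The interruption route is partly visible already.** Protocol 10.1.1 provides for interruption only for specific hyperprolactinemia-related AESI. Those AEs enter the AESI table, and the named ones that persist or recur on re-challenge lead to mandatory discontinuation under Protocol 13.1. This stands in part. The AESI table shows that the AE occurred, not that dosing was interrupted, and it says nothing about dose reductions.
- **SAP 4.7 claims only to list the main changes, and the table templates might show more.** SAP 9 refers to templates that are not among the documents reviewed. This stands as a limit on the finding: absence is established for the SAP text only.
- **With 64 enrolled, listings may suffice.** That is a fair argument for a shorter display. However, the SAP keeps SOC and preferred-term tables by severity at the same sample size, so size alone does not explain dropping this one.

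A reader might go further and infer that the tables will make the drug look better tolerated than the data show. The documents do not support that. No AE count falls, and the discontinuation rate is reported as what it is. Nor can the gap be put in percentage points. The documents do not give the number of such AEs, their overlap with discontinuations, the number of subjects who reached 400 mg/day (only they can have a reduction, since 200 mg/day is the minimum), or the size of the Safety Population. The figure of 64 counts enrolled subjects, whom SAP 6 defines by signed consent.

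**Conclusion.** The point holds as an undeclared departure from the protocol that removes a pre-specified tolerability display. Two of four planned AE breakdowns are missing from the SAP. One of them, action taken, is the only planned summary that would connect AEs to dose reduction or interruption. The loss by outcome is the same kind of gap and matters less, because deaths are still tabulated.

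The consequence is loss of information, not bias: no endpoint and no AE count changes, and the study is descriptive throughout. The conclusion assumes that the unseen templates do not already contain the table and that listings are not offered as its replacement. If the templates do contain it, what remains is to make the SAP text match them.

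**What to change.** 1. In SAP 18.1.1, restore the summary of AEs by SOC and preferred term by action taken. The existing SAP 18.1 rule, which counts a subject once within each category, can apply. A subject may then appear under more than one action, and a footnote should say so.
2. If the full table is judged too sparse, add at least two rows to the overall AE summary: AEs with action Dose Reduced and AEs with action Drug Interrupted. Show both by PBO-SEP, SEP-SEP and ALL EXT, with the Safety Population as denominator. Read the reduction row beside the SAP 15 count of subjects exposed to 400 mg/day.
3. List in SAP 4.7, with a reason, any breakdown that stays dropped, including outcome.
4. State that action taken is a column in the AE listings.

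The cost is a few lines of SAP text and one table, or two rows, from a field already collected. Study conduct does not change. If the SAP is no longer open to revision, the same output can be added as a documented change in the study report.

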#### 18.1.1.1. Severity

Severity is classed as mild/ moderate/ severe (increasing severity). AEs with a missing severity will be classified as severe.

If a subject reported an AE more than once within the same SOC/ PT with different severity levels, the

subject will be assigned to a severity level for that SOC/ PT based on the worst case severity (i.e., maximum severity). Event counts will not be included in this summary.

In a separate table, severe AEs will be summarized by SOC and PT.

#### 18.1.1.2. Relationship to study medication

Relationship to study medication, as indicated by the Investigator, is classed as "not related"/ "possible"/ "probable"/ "definite" (increasing strength of relationship). A "related" AE is defined as an AE with a relationship to study medication as "possible", "probable" or "definite". AEs with a missing relationship to study medication will be regarded as related to the study medication. For this summary, AEs will be presented in 2 categories, related and not related.

If a subject reported an AE more than once within the same SOC/ PT in different relationship categories, the subject will be assigned to a category for that SOC/ PT based on the worst case relationship (i.e., strongest relationship). Event counts will not be included in this summary.

#### 18.1.2. AEs LEADING TO DISCONTINUATION FROM STUDY

AEs leading to discontinuation from the study are those AEs with "Caused Study Discontinuation" = "Yes" on the "Adverse Events" CRF form for subjects with reason for discontinuation as AE on the Study Disposition CRF page or AE action taken = "Drug Withdrawn".

AEs leading to discontinuation from the study will be summarized by SOC and PT. A listing of AEs leading to discontinuation from the study treatment period will be presented.

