12.3. Collection and Recording of Adverse Events

All AEs must be recorded in the subject's study records/source documents in accordance with the Investigator's normal clinical practice. All AEs that occur from the signing of the informed consent to the subject's last visit must be recorded on the eCRF.

All AEs will be followed until resolution, stabilization of the condition, the event is otherwise explained, or the subject is lost to follow-up.

Each AE is to be evaluated for duration, severity, frequency, seriousness, action taken with the study treatment, outcome, and causal relationship to the study treatment. Definitions for severity, frequency, action taken with the study treatment, outcome, and causal relationship to the study treatment are presented below.

The severity of AE:

- **Mild** Ordinarily transient symptoms that do not influence performance of subject's daily activities. Other treatment is not ordinarily indicated.
- **Moderate** Marked symptoms sufficient to make the subject uncomfortable. Moderate influence on performance of subject's daily activities. Other treatment may be necessary.
- Severe Symptoms cause considerable discomfort. Substantial influence on subject's daily activities. May be unable to continue the study, and other treatment may be necessary.

The frequency of AE:

- **Once** an isolated episode
- Intermittent occurs on two or more separate occasions
- **Continuous** does not abate from date of onset to date of resolution

The action taken with the study treatment:

- **Drug Interrupted** Study drug stopped temporarily.
- Drug Withdrawn Study drug stopped permanently.
- Dose Reduced
- Dose Increased
- Dose Not Changed
- Not Applicable
- Unknown

The outcome of the AE:

- Recovered/Resolved
- Recovering/Resolving
- Not Recovered/Not Resolved
- Recovered/Resolved with Sequelae
- Fatal
- Unknown

The causal relationship of the AE to the study treatment: Not related

- **Not related -** Improbable temporal relationship and is plausibly related to other drugs or underlying disease.
- Related
 - **Possible** occurred in a reasonable time after study drug administration, but could be related to concurrent drugs or underlying disease.
 - **Probable** occurred in a reasonable time after study drug administration, is unlikely to be attributable to concurrent drugs or underlying disease, and there is a plausible mechanism to implicate the study drug.

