13. TERMINATION OF SUBJECT FROM STUDY/DISCONTINUATION OF STUDY DRUG

13.1. Criteria for Subject Termination

Subjects may terminate the study participation at any time for any reason.

The possible reasons for the termination of study participation are as follows:

- Adverse event
- Lack of efficacy (specify)
- Lost to follow-up (specify)
- Pregnancy
- Withdrawal of consent (specify)
- Non-compliance with study drug (specify)
- Protocol deviation (specify)
- Death
- Other (specify)

If at any time during the course of the study, in the opinion of the Investigator, the subject may no longer safely participate due to a change in medical status (eg, experiences an AE, becomes pregnant), the subject must be discontinued from the study.

Discontinuation due to AE with follow-up until resolution is mandatory in the following cases:

- Subject who, at any study visit post-Baseline, has a QTcF interval > 500 msec, or who has a ≥ 60 msec increase in QTcF from Baseline (machine reading or centrally overread report), or who experiences a life-threatening cardiac arrhythmia must be discontinued from the study, referred to the Investigator for follow-up evaluation, and followed until the event resolves; in addition, an associated AE must be reported.
- Subject who develops an AE of amenorrhea (missed menses for a minimum of 3 months), symptomatic gynecomastia, or galactorrhea that does not resolve within 2 weeks of study drug interruption or that recurs with re-challenge must be discontinued from the study, referred to the Investigator for follow-up evaluation, and followed until the event resolves.
- Subject who answers "yes" to "suicidal ideation" item 4 (active suicidal ideation with some intent to act, without specific plan) or item 5 (active suicidal ideation with specific plan and intent) on any post-Baseline C-SSRS assessment must be discontinued from the study, referred to the Investigator for follow-up evaluation, and followed until the event resolves; in addition, an associated AE must be reported.
- Subjects who require hospitalization/prolonged hospitalization for treatment of COVID-19-related illness will be discontinued. Subjects with an active COVID-19 infection should be discussed on a case-by-case basis with the IQVIA Medical

Monitor to obtain agreement on whether a subject with an active COVID-19 infection should be discontinued.

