The reason for termination of study participation and information on the epoch will be recorded on the appropriate eCRF. In case of death, the date of death should be captured on the eCRF.

Subjects who prematurely terminate the study participation will not be replaced.

Subjects who discontinue prior to Visit 14E (Month 12) will undergo procedures and assessments scheduled for Visit 14E (Month 12) at the time of early discontinuation (see Section 11.6.14).

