17.3. Informed Consent

The Investigator will prepare the informed consent form and provide the form to Sponsor/CRO for approval prior to submission to the IRB/IEC. The informed consent form will be approved by the Sponsor/CRO prior to submission to the IRB/IEC. The Sponsor/CRO may provide a template informed consent form to be qualified by each research facility to conform to local requirements. All informed consent forms must contain the minimum elements as mandated by ICH GCP, applicable local law(s) and regulations and will be subject to Sponsor/CRO approval as well as IRB/IEC approval. The Sponsor/CRO may submit informed consent forms to a central IRB/IEC for review and approval or favorable opinion contingent upon prior Investigator permission and review.

Before recruitment and enrollment, each prospective subject will be given a full explanation of the study, allowed to read the approved informed consent form, and be provided ample time and the opportunity to ask any questions that may arise. Once all questions have been answered and the Investigator is assured that the prospective subject understands the implications of participating in the study, the prospective subject will be asked to give consent to participate in the study by signing the informed consent form. As part of the consent process, each prospective subject must consent to direct access to his/her medical records for study-related eligibility, monitoring, auditing, IRB/IEC review, and regulatory inspection. It should be clearly explained to each prospective subject that participation in each and every clinical visit and assessment is expected. The subject may be discontinued from study medication, but that does not necessarily negate the expectation that the subject will continue to participate in the study through the final visit/assessment. The Investigator will provide a copy of the signed informed consent form to each subject and will record the date of the informed consent on the eCRF.

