## **3.2. STUDY ENDPOINTS**

### **3.2.1. PRIMARY ENDPOINTS**

- The incidence of overall AEs, discontinuation due to AEs, and SAEs

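### The SAP rule for AEs leading to discontinuation, part of the primary endpoint, can be read two ways, and both readings omit a narrow set of AEs that the investigator flagged as causing discontinuation

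*SAP*

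**What the plan says.** SAP 3.2.1 gives the primary endpoint as "The incidence of overall AEs, discontinuation due to AEs, and SAEs". SAP 18.1.2 supplies the operational rule for the middle component. It opens with "AEs leading to discontinuation from the study are those AEs with 'Caused Study Discontinuation' = 'Yes", continues "for subjects with reason for discontinuation as AE on the Study Disposition CRF page or AE action taken", and ends by naming Drug Withdrawn as the action. Three items are therefore combined:

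- **C**: the AE form's flag for having caused study discontinuation is Yes.
- **D**: the subject's reason on the disposition page is adverse event.
- **W**: the AE's action taken is Drug Withdrawn, which Protocol 12.3 explains as "Study drug stopped permanently".

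Protocol 13.1 introduces the disposition reasons with "The possible reasons for the termination of study participation are as follows". Death, lack of efficacy, withdrawal of consent and other reasons are entries separate from adverse event. The same section says "The reason for termination of study participation and information on the epoch will be recorded on the appropriate eCRF"; the singular suggests one reason per subject, although the CRF page itself is not in the documents. Besides Drug Withdrawn, Protocol 12.3 allows an action of interrupted, dose reduced, dose increased, dose not changed, not applicable or unknown.

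Protocol 15.4.3.1 plans a summary of AEs leading to discontinuation without tying it to the disposition page. SAP 4.7, which lists the main changes from the protocol, does not mention this rule.

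**The concern.** There are two separate problems. First, the 'or' before W can attach to D alone or to the whole of what precedes it, so two programmers working correctly from the same sentence can produce different counts for a component of the primary endpoint. Second, under either reading the disposition page can overrule an explicit Yes from the investigator on the AE form. The neighbouring rules go the other way: SAP 18.1.1.1 classes a missing severity as severe and SAP 18.1.1.2 treats a missing relationship as related, so doubt is settled towards counting.

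The split between stopping drug and leaving the study, on which the first problem turns, is foreseen in Protocol 17.3: "The subject may be discontinued from study medication, but that does not necessarily negate the expectation that the subject will continue to participate". An AE could therefore have action Drug Withdrawn without being flagged as the cause of study discontinuation.

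**Working it through.** The documents give no figure to reproduce, since this is a rule of logic. The check is to apply both readings, and the proposed rule, to every combination of C, D and W.

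- Reading 1: (C and D) or W
- Reading 2: C and (D or W)
- Proposed: C or W

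| C (flag) | D (reason is AE) | W (Drug Withdrawn) | Reading 1 | Reading 2 | Proposed |
|---|---|---|---|---|---|
| Yes | Yes | Yes | counted | counted | counted |
| Yes | Yes | No | counted | counted | counted |
| Yes | No | Yes | counted | counted | counted |
| Yes | No | No | omitted | omitted | counted |
| No | Yes | Yes | counted | omitted | counted |
| No | Yes | No | omitted | omitted | omitted |
| No | No | Yes | counted | omitted | counted |
| No | No | No | omitted | omitted | omitted |

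Three things follow.

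1. The readings disagree in two of the eight rows, both with C = No and W = Yes. The ambiguity therefore matters only for AEs for which drug was permanently stopped but the flag is not Yes.
2. One row with C = Yes is lost under both readings: C = Yes, D = No, W = No. An example is a fatal AE that is flagged, with disposition reason Death and action Not Applicable. This gap comes from the disposition condition and not from the missing bracket, so adding a bracket would leave it open.
3. A flagged AE with action Drug Withdrawn is counted under both readings whatever the disposition reason.

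For size, SAP 4.4 reports 64 enrolled. The SAP does not state the Safety Population count, so I assume it equals 64. One subject is then 1/64 = 1.56 percentage points in ALL EXT; two are 2/64 = 3.1 and three are 3/64 = 4.7. Within PBO-SEP or SEP-SEP each subject weighs more, but those group sizes are not given.

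**The case against.** The best counter-argument is that the records at risk are unusual. For a flagged AE to be lost, three things must hold together: flag Yes, disposition reason not AE, and action not Drug Withdrawn. Apart from deaths, that is close to a contradictory record, because an AE that ended participation would normally carry the action for permanent stopping. This stands, and it limits how often the gap will matter.

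It also rules out a stronger inference that a reader might draw: that the count turns on the disposition reason alone, so that, for example, a worsening-mood AE filed under lack of efficacy would drop out and the rate would be understated by some sizeable fraction. The documents do not support this. If that AE is flagged and its action is Drug Withdrawn, both readings count it.

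Second, fatal AEs do not disappear. SAP 18.1 gives AEs leading to death their own line in the overall summary and their own listing, and SAP 18.1.3 includes them in the SAE tables. SAEs are part of the same primary endpoint. This stands too: what can be lost is the entry in the discontinuation count. Recording Not Applicable for a death is itself only a plausible assumption.

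Third, the protocol largely couples stopping drug with leaving the study. Section 13 treats them under one heading, early terminators have the Visit 14E procedures at that time, and follow-up is 7 ± 2 days after the last dose. Since 18.1.2 is titled as discontinuation from study, leaving out an AE that stopped drug only would suit the title, which favours Reading 2. That is a fair argument for one reading, but it shows that a choice is needed; the sentence does not make it.

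Finally, the study makes no inference (SAP 7.6), all these AEs are listed, and a pre-lock data review is planned (SAP 2). These facts lower the stakes but do not settle which number goes in the table.

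**Conclusion.** The point holds in a limited form. As written, SAP 18.1.2 does not determine the count for Drug Withdrawn AEs that lack the flag. Under both readings it also leaves out a flagged AE whose disposition reason is not AE and whose action is not Drug Withdrawn. No other section of the protocol or SAP resolves either matter.

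Each affected subject changes the ALL EXT rate by about 1.6 percentage points, assuming the Safety Population is the 64 enrolled. The documents do not show how many subjects are affected, and it could be none. No relative understatement can be stated. That one disposition reason is recorded per subject is inferred from the singular wording in Protocol 13.1. It is worth correcting because the count belongs to the SAP's primary endpoint and the correction is small.

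**What to change.** - In SAP 18.1.2, define the endpoint as any AE with the caused-study-discontinuation flag equal to Yes, or with action taken Drug Withdrawn, regardless of the disposition reason. This removes the ambiguity and closes the gap for flagged AEs.
- Because the rule then covers both events, title the table as discontinuation of study or study drug, or show the two components as separate rows.
- Add a listing for reconciliation before database lock of subjects whose AE and disposition pages disagree. It should include fatal AEs with the flag unticked, because the new rule would still miss such an AE if its action is not Drug Withdrawn. It should also include subjects whose disposition reason is AE but who have no AE that is flagged or has action Drug Withdrawn.

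The cost is one sentence, a title or row change and one listing. The drawback is that the count may not equal the adverse-event row of the disposition table in SAP 10; a footnote can explain the difference.
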